5.3.3 Safety laboratory parameters

For the visit schedule requiring safety laboratory sampling, see the Flow Charts. The laboratory tests listed in [Table 5.3.3: 1](#) will be performed at the central laboratory service provider. A local laboratory may be used for selected tests in exceptional cases. Patients should be fasting for at least 8 hours prior to the blood sample being taken (except screening visit).

Instructions regarding sample collection, sample handling/ processing and sample shipping are provided in the Laboratory Manual in the ISF.

Laboratory results (i.e. all safety laboratory and clinical laboratory data relevant for current clinical practice of psoriasis patients) of the patients will be available in real time to the respective investigator (via laboratory reports) and to the sponsor (via the central laboratory website) and selected abnormal laboratory alerts will be flagged to the site and sent to sponsor in real time.

Clinically relevant abnormal findings will be reported as baseline conditions or AE's. A clinically relevant value may be either inside or outside the reference range. Clinically relevant abnormal laboratory test results must be confirmed using an unscheduled visit laboratory kit and should be repeated until normalisation or stabilisation or until an alternative explanation has been found. Abnormal laboratory values will be also graded for intensity by using RCTC Version 2.0 criteria ([R13-3515](#)).

Proprietary confidential information © 2016 Boehringer Ingelheim International GmbH or one or more of its affiliated companies
 Table 5.3.3:1 Laboratory tests

Category	Test name
Haematology	Hematocrit (Hct) Hemoglobin (Hb) Glycosylated Hb (HbA1c) Red Blood Cell Count/ Erythrocytes Reticulocyte Count White Blood Cells / Leukocytes Platelet Count/ Thrombocytes
Diff. Automatic	Neutrophils (relative and absolute count) Eosinophils (relative and absolute count) Basophils (relative and absolute count) Monocytes (relative and absolute count) Lymphocytes (relative and absolute count)
Diff. Manual (if Diff Automatic is abnormal)	Neutrophils, bands (Stabs) Neutrophils, polymorphonuclear (PMN) Eosinophils Basophils Monocytes Lymphocytes
Coagulation	Activated Partial Thromboplastin Time (aPTT) Prothrombin time (INR) Fibrinogen
Enzymes	AST(GOT) ALT(GPT) Alkaline Phosphatase (AP) Creatine Kinase (CK) CK-MB, (Only if CK is elevated) Gamma-Glutamyl Transferase (GGT/γ-GT) Lactic Dehydrogenase (LDH) Amylase Lipase

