Electrolytes	Calcium Sodium Potassium Chloride Bicarbonate
Substrates	Glucose BUN Uric acid Creatinine eGFR (estimated by CKD-EPI formula) Bilirubin Total Bilirubin Direct (if total is elevated) Bilirubin Indirect (if total is elevated) Troponin (Reflex when CK is elevated) Albumin C-Reactive Protein (high sensitivity) Cholesterol, total Triglycerides LDL-Cholesterol (calculated) HDL-Cholesterol HOMA-IR (V2, V9, V15, V19, EOO)
Urine Pregnancy test ¹	Human Chorionic Gonadotropin in the urine
Serum Pregnancy test ²	Human Serum Chorionic Gonadotropin

Proprietary confidential information © 2016 Boehringer Ingelheim International GmbH or one or more of its affiliated companies
 Table 5.3.3:1 Laboratory tests

Category	Test name
Hormones (screening)	TSH, (free T3 and free T4 in case of abnormal TSH results)
Autoantibodies (screening)	Rheumatoid Factor
Urinalysis (Stix)	Urine Nitrite Urine Protein Urine Glucose Urine Ketone Urobilinogen Urine Bilirubin Urine RBC/ Erythrocytes Urine WBC/ Leukocytes Urine pH
Urine-Sediment (microscopic examination, only if urine analysis abnormal)	Urine Sediment Bacteria Urine Cast in Sediment Urine Squamous Epithelial Cells Urine Sed. Crystals., Unspecified Urine Sediment RBC/ Erythrocytes Urine Sediment WBC/ Leucocytes
Urinalysis	Albumin (quantitative) Creatinine Albumin/Creatinine ratio
Infection Testing (Screening ³ V15, EOO)	Hepatitis B Surface Antigen (qualitative) Hepatitis C Antibodies (qualitative) HIV-1, and HIV-2 Antibody (qualitative) QuantiFERON®-TB ³

1. Urine pregnancy test performed on-site at all dosing visits (pre-dose) as well as EOT and EOO. (**only for female patients of childbearing potential**)
2. Serum pregnancy test at screening as well as confirmation of positive urine pregnancy test. (**only for female patients of child bearing potential at screening as well as reflex for positive urine pregnancy test**)
3. **At Screening only TB testing is required.** There is the site option to perform a PPD skin test, although this will not be provided or performed at Central Lab

5.3.4 **Electrocardiogram**

The 12-lead ECGs will be performed as scheduled in the Flow Chart(s).

ECGs will be recorded after the patients have rested for at least 5 minutes in a supine position and will always precede blood sampling. Six limb leads, as specified by Einthoven (I, II and III) and Goldberger (aVR, aVL, aVF), and six pre-cordial leads (V1–V6), according to Wilson, will be used.

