7.3.4 Safety analyses

Adverse events will be coded using the Medical Dictionary for Drug Regulatory Activities (MedDRA) coding dictionary. Standard AbbVie summary tables and listings will be produced. All adverse events with an onset between start of treatment and end of the residual effect period (REP), a period of 15 weeks days after the last dose of trial medication, will be assigned to the treatment period for evaluation.

All treated patients will be included in the safety analysis. In general, safety analyses will be descriptive in nature and will be based on AbbVie standards. No hypothesis testing is planned.

Statistical analysis and reporting of adverse events will concentrate on treatment-emergent adverse events. To this end, all adverse events occurring between start of treatment and end of the residual effect period will be considered 'treatment-emergent'. Adverse events that start before first drug intake and deteriorate under treatment will also be considered as 'treatment-emergent'.

Frequency, severity, and causal relationship of adverse events will be tabulated by system organ class and preferred term after coding according to the current version of the Medical Dictionary for Drug Regulatory Activities (MedDRA).

Laboratory data will be analysed both quantitatively as well as qualitatively. The latter will be done via comparison of laboratory data to their reference ranges. Values outside the reference range as well as values defined as clinically relevant will be highlighted in the listings.

Treatment groups will be compared descriptively with regard to distribution parameters as well as with regard to frequency and percentage of patients with abnormal values or clinically relevant abnormal values.

Vital signs, physical examinations, or other safety-relevant data observed at screening, baseline, during the course of the trial and at the end-of-trial evaluation will be assessed with regard to possible changes compared to findings before start of treatment.

More information on the analysis of safety will be given in the TSAP.

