Section to be changed	4.2.2.3 Restrictions regarding women of childbearing potential
Description of change	Deleted reference to Section 3.3.3, and corrected to 3.3.2
Rationale for change	Error in original protocol
Section to be changed	5.1.3 Further endpoints
Description of change	Text added “The above endpoints will be analyzed,

Proprietary confidential information © 2016 Boehringer Ingelheim International GmbH or one or more of its affiliated companies

		where appropriate, for re-randomized subjects after receiving open-label study drug for retreatment (Flow Chart 2 and 3)".
Rationale for change		To clarify that these endpoints will also be analyzed among retreatment patients at visits collected.
Section to be changed		5.3.2 Vital Signs
Description of change		The underlined wording was added to the following sentences. "In addition at Visit 2 and Visit 3 vital sign evaluations will be taken at approximately 5 minutes post-dose (5 minutes after last injection) and approximately 60 minutes post-dose (60 minutes after last injection). Patients should be closely monitored for signs and symptoms of hypersensitivity reactions for approximately 2 hours after the last injection at Visit 2 and for approximately one hour after the last injection at all other visits where drug is administered
Rationale for change		To specify timing of vitals relative to injection times and also timing of monitoring hypersensitivity with respect to injection times.
Section to be changed		Table 5.3.3:1 laboratory tests
Description of change		Added absolute count to differential Added "activated to aPTT Deleted "MB" from Troponin reflex Added "calculated" to LDL Deleted "creatinine" from urinalysis stix Added "creatinine" to urinalysis Added Albumin/creatinine ratio to Urinalysis
Rationale for change		Was omitted from original CTP or needed further clarification
Section to be changed		6.2 Details of Trial Procedures At Selected Visits
Description of change		Added paragraph to note that efficacy questionnaires are direct data capture on an electronic device
Rationale for change		Omitted from original CTP
Section to be changed		Section 6.2.2, Week 28 Visit and Randomized withdrawal period (Re-randomized patients)
Description of change		Wording revised due to implementation of continuing blinded treatment
Rationale for change		Design change for Week 28
Section to be changed		Section 6.2.2 Treatment period

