3.0 Introduction

This statistical analysis plan (SAP) describes the statistical analysis to be completed by the AbbVie Clinical Statistics Department for study Protocol 1311.4 dated 28 July 2016.

This SAP will provide details to further elaborate statistical methods as outlined in the Protocol 1311.4 and will describe analysis conventions to guide the statistical programming work. The SAP will be signed off before the study database is locked.

Analyses will be performed using SAS® version 9.4 (SAS Institute, Inc., Cary, NC 27513) or higher using the UNIX operating system.

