11.3.1 Variables and Criteria Defining Abnormality

Clinical laboratory tests conducted in the study are listed in [Table 24](#).

Table 24. Clinical Laboratory Tests

Category	Test Name
Haematology	Hematocrit (Hct) Hemoglobin (Hb) Glycosylated Hb (HbA1c) White Blood Cells/Leukocytes Platelet Count/Thrombocytes
Diff. Automatic	Neutrophils (relative and absolute count) Eosinophils (relative and absolute count) Lymphocytes (relative and absolute count)
Enzymes	AST (GOT) ALT (GPT) Alkaline Phosphatase (AP) Creatine Kinase (CK) Gamma-Glutamyl Transferase (GGT/γ-GT) Lactic Dehydrogenase (LDH) Amylase Lipase
Electrolytes	Calcium Sodium Potassium
Substrates	Glucose BUN Uric acid Creatinine eGFR (estimated by CKD-EPI formula) Bilirubin Total Albumin C-Reactive Protein (high sensitivity) Cholesterol, total Triglycerides LDL-Cholesterol (calculated) HDL-Cholesterol
Urinalysis (Stix)	Urine Protein Urine Glucose

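### SAP Table 24 omits 19 routine laboratory tests that the protocol schedules and does not declare the reduction, so the SAP specifies no test-level summary by arm for them

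*Protocol*

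**What the plan says.** **Protocol.** Table 5.3.3:1 (section 5.3.3) sets out the laboratory tests. It includes a coagulation panel ("Activated Partial Thromboplastin Time (aPTT) Prothrombin time (INR) Fibrinogen"), a five-part automatic differential with "Basophils (relative and absolute count) Monocytes (relative and absolute count", and a quantitative urine panel ("Albumin (quantitative) Creatinine Albumin/Creatinine ratio"). The log of Amendment 2 in section 11 records when the ratio came in: "Added Albumin/creatinine ratio to Urinalysis". Section 7.3.4 says "Laboratory data will be analysed both quantitatively as well as qualitatively". It adds that values will be set against reference ranges, and that treatment groups will be compared descriptively on distribution and on the frequency of abnormal values. No subset of tests is named.

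**SAP.** Section 3.0 says the plan is for "study Protocol 1311.4 dated 28 July 2016", which is Amendment 2. Section 11.3 opens with a general promise of listings and descriptive statistics of laboratory values. Section 11.3.1 then defines the tests: "Clinical laboratory tests conducted in the study are listed in" Table 24. The change-from-baseline methods in section 11.3.2 fall under a heading for hematology and chemistry, and the shift tables are promised for parameters of those two classes. Section 14.1 lists four changes from the protocol, and a shorter laboratory list is not one of them.

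**The concern.** Table 24 is worded as the complete set of tests done in the trial, and against the protocol it is not. A programmer following the SAP would produce change-from-baseline and shift tables for the listed tests only. A reader of the report could then take a selected subset for the whole laboratory safety assessment.

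At stake is the ability to see a shift in distribution between arms for coagulation, monocytes or quantitative albuminuria. These data are already collected. The comparisons affected are Safety_A1 (risankizumab against placebo to Week 16) and Safety_B_R (continued drug against withdrawal to placebo), together with the pooled ALL_RZB summaries. An undeclared reduction also leaves the sponsor open to the question of whether tests were dropped after results were known.

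**Working it through.** The documents state no count of omitted tests, so there is no figure to reproduce. The check is an item-by-item comparison of protocol Table 5.3.3:1 with SAP Table 24.

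**Excluded from the count.** Reflex or conditional tests: 6 manual differential + 1 CK-MB + 2 direct and indirect bilirubin + 1 troponin + 6 urine sediment = 16. Screening-only hormone and autoantibody tests, pregnancy tests and infection tests are also left out.

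| Category | Protocol, routine | SAP Table 24 | Missing |
|---|---|---|---|
| Haematology | 7 | 5 | 2 (red cells, reticulocytes) |
| Automatic differential | 5 | 3 | 2 (basophils, monocytes) |
| Coagulation | 3 | 0 | 3 (aPTT, INR, fibrinogen) |
| Enzymes | 8 | 8 | 0 |
| Electrolytes | 5 | 3 | 2 (chloride, bicarbonate) |
| Substrates | 13 | 12 | 1 (HOMA-IR) |
| Dipstick | 9 | 2 | 7 (nitrite, ketone, urobilinogen, bilirubin, red cells, white cells, pH) |
| Quantitative urine | 3 | 0 | 3 (albumin, creatinine, ratio) |
| **Total** | **53** | **33** | **20** |

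All 33 SAP tests are in the protocol table. HOMA-IR is accounted for, because SAP section 4.1 places metabolic risk factor analyses outside the plan. That leaves 20 − 1 = 19.

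**Do the methods reach these tests?** Six of the 19 (red cells, reticulocytes, basophils, monocytes, chloride, bicarbonate) are haematology or chemistry, so the section 11.3.2 methods would apply once they were in Table 24. The other 13 (3 coagulation + 7 dipstick + 3 quantitative urine) fall outside the classes that section 11.3.2 names. Adding rows to Table 24 would not be enough for them.

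**Is the version right?** The SAP cites 28 July 2016, the date of Amendment 2. The log of Amendment 3 (11 October 2016) lists no change to the laboratory table, so the current table is the one the SAP should match.

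**The case against.** The strongest case on the other side is that this is a small documentation gap.

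- **Listings remain.** The opening of SAP section 11.3 is not worded as limited to Table 24, protocol section 7.3.4 keeps its listings with out-of-range values highlighted, and SAP section 17.0 puts the list of outputs in a separate document that is not available here. This stands. A reader might infer that these tests get no output at all, and the documents do not support that. They support only the absence of a specified test-level summary.
- **Adverse events and liver tests remain.** Clinically relevant abnormal findings become baseline conditions or adverse events. The hepatic search in SAP Table 23 includes liver-related coagulation and bleeding terms. ALT, AST and bilirubin have their own summaries and a Hy's Law listing. It is tempting to add that the protocol's hepatic injury rule depends on INR. It does not: section 5.3.6.1 mentions coagulopathy as a clinical symptom, then asks for ALT, AST and total bilirubin. Even so, adverse event reporting depends on a judgement of clinical relevance and cannot show a shift in distribution.
- **Renal measures remain.** Dipstick protein, creatinine, BUN and eGFR are in Table 24, so albuminuria is not wholly unobserved. Dipstick protein is coarser than the ratio, however, and urinalysis is not named in the shift-table sentence.
- **The protocol leaves detail to the SAP.** Section 7.3.4 refers to company standards and the later plan, and section 5.3 names haematology, clinical chemistry and urinalysis without coagulation. This is fair, but neither passage removes a test, and coagulation is in the safety laboratory table. Where the SAP does depart from the protocol on laboratory grading, section 11.3.2 says so and gives a reason.
- **Some of the 19 are minor.** Seven are dipstick items, and the three quantitative urine tests describe one quantity. This stands, and the fix allows for it.

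**Conclusion.** The point holds as a conflict between current protocol Table 5.3.3:1 and section 7.3.4 on one side and SAP sections 11.3.1, 11.3.2 and 14.1 on the other. Nineteen routine tests have no test-level summary by arm specified in the SAP, the sentence introducing Table 24 is wrong against the protocol, and the reduction is undeclared. It should be corrected, but it touches no efficacy, power or alpha figure.

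Three stronger readings are not supported:

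- That the SAP failed to follow Amendment 2. The log gives a housekeeping reason for its laboratory edits ("Was omitted from original CTP or needed further clarification"), and 18 of the 19 omissions do not depend on the ratio.
- That the only placebo comparison is lost. SAP section 11.1 compares risankizumab with placebo in both Safety_A1 and Safety_B_R.
- That a safety signal is being missed. The documents identify none for any of the 19 tests.

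The count assumes that reflex, screening-only, pregnancy and infection tests, and HOMA-IR, are rightly set aside; with HOMA-IR it would be 20. The conclusion also assumes that the separate list of outputs follows Table 24, which cannot be checked.

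**What to change.** Before database lock, and preferably before the lock for the Week 52 analysis, at which protocol section 7.4 unblinds the sponsor:

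1. Add at least aPTT, INR, fibrinogen, monocytes, basophils, red cells, reticulocytes, chloride, bicarbonate and the urine albumin/creatinine ratio to SAP Table 24.
2. Extend the change-from-baseline and shift-table wording in section 11.3.2 to coagulation and quantitative urinalysis, for Safety_A1, Safety_B_R and ALL_RZB.
3. Correct the sentence in section 11.3.1 so that Table 24 is described as the tests to be summarised.
4. Declare in section 14.1, with the reason, any test that will be listed only, such as the minor dipstick items.

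No new data are needed, and the existing programs can produce the extra rows. The cost goes a little beyond length. SAP section 11.1 compares arms by ANOVA or Fisher's exact test in Safety_A1 and Safety_B_R, so ten added tests bring at least 10 × 2 = 20 further unadjusted comparisons if each is compared once per population. They should be read as descriptive, in keeping with protocol section 7.3.4, which plans no hypothesis testing for safety.

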3.0 Introduction

This statistical analysis plan (SAP) describes the statistical analysis to be completed by the AbbVie Clinical Statistics Department for study Protocol 1311.4 dated 28 July 2016.

This SAP will provide details to further elaborate statistical methods as outlined in the Protocol 1311.4 and will describe analysis conventions to guide the statistical programming work. The SAP will be signed off before the study database is locked.

Analyses will be performed using SAS® version 9.4 (SAS Institute, Inc., Cary, NC 27513) or higher using the UNIX operating system.

4.0 Study Objectives, Design and Procedures

4.1 Primary Study Objective

The primary objective of the initial randomized phase of the study (Part A1; see Section 4.2) is to assess the efficacy of risankizumab 150 mg in comparison to placebo in subjects with moderate to severe chronic plaque psoriasis. The primary objective of the second randomized phase of the study (Part B; see Section 4.2) is to evaluate the maintenance of response with continuous risankizumab treatment compared with withdrawal of treatment.

The primary efficacy evaluation will be performed at 16 weeks. The maintenance of response following drug withdrawal will be assessed after Week 28 through the end of the study (primary evaluation at Week 52). Subsequent to drug withdrawal, subjects who experience relapse will be retreated with risankizumab to assess response after retreatment.

Evaluations of risankizumab efficacy and safety in various populations will be performed in the study to provide a full picture of risankizumab benefits and risks. These populations and the intent of the related analyses is specific in Section 5.2.

In addition, this trial will assess pharmacokinetics (PK) and the emergence of anti-drug antibodies (ADA) and their effect on efficacy and safety. Moreover, it will be explored how the use of risankizumab may influence gene and protein expression levels and disease specific protein markers. PK and ADA analyses, as well as DNA banking, exploratory biomarker, and metabolic risk factor analyses, will not be included in this SAP.

4.2 Design Diagram

This is a confirmatory, multinational, multicenter, randomized, double-blind, placebo controlled study with randomized withdrawal and retreatment, evaluating the safety and efficacy of risankizumab 150 mg subcutaneous (SC) in patients with moderate to severe chronic plaque psoriasis.

The study consists of an up to 42 day screening period, a 16-week double-blind, placebo-controlled initial treatment period (Part A1), a 12-week treatment period (Part A2), an up to 60-week continuous treatment and treatment withdrawal period (Part B) with possible retreatment with risankizumab for up to 16 weeks, and a 16 week follow-up period.

Part A1: A 16-week double-blinded, placebo-controlled treatment period during which subjects will be randomized at a ratio of 4:1 to one of two treatment arms as shown in [Figure 1](#). Arm 1 refers to those subjects originally randomized to risankizumab and Arm 2 refers to those subjects originally randomized to placebo. The first dose of study drug will be administered on Day 1 (Visit 2; Baseline) and the second dose will be administered at Week 4. The randomization will be stratified with respect to weight (≤ 100 kg vs. > 100 kg) and prior exposure to TNF antagonists (0 vs. ≥ 1).

[figure not shown]
Part A2: A 12-week treatment period. At Week 16, all subjects will receive one dose of risankizumab 150 mg.

Part B: At Week 28, non-responders (static Physician Global Assessment [sPGA] ≥ 2) will receive open label risankizumab 150 mg every 12 weeks with a last dose at Week 88 (end-of-treatment, EOT), while responders (sPGA of 0 or 1) from Arm 1 will be

re-randomized in a 1:2 ratio to either maintain risankizumab 150 mg or matching placebo every 12 weeks with a last dose at Week 88 (EOT). The re-randomization will be stratified with respect to weight (≤ 100 kg vs. > 100 kg) and prior exposure to TNF antagonists (0 vs. ≥ 1). Responders from Arm 2 will continue to receive blinded risankizumab 150 mg every 12 weeks with a last dose at Week 88 (EOT) to maintain the blind. Throughout the SAP, "re-randomized" or "re-randomization" refers to the randomization at Week 28 among subjects from Arm 1 of Part A.

Retreatment: Starting from Week 32, subjects experiencing relapse (defined as an sPGA of ≥ 3), will receive open label risankizumab 150 mg. If this relapse occurs anytime between Week 32 through Week 70, open label risankizumab 150 mg will be administered at 0, 4, and 16 weeks (EOT) after relapse. If this relapse occurs after Week 70 through Week 82, open label risankizumab 150 mg will be administered 0 and 4 weeks (EOT) after relapse. If the relapse occurs after Week 82 through Week 88 the subject will immediately have the EOT procedures performed, including the final dose of study drug.

Follow-Up Period: Subjects who have completed their EOT visit will be followed up for 16 weeks. Follow-up Visit 1 is scheduled at 6 weeks after EOT. And Follow-up Visit 2 is scheduled at 16 weeks after EOT, which is the end of observation (EOO) visit. Subjects who have completed the EOO visit within the specified window, who have not discontinued drug prematurely, and who also meet the eligibility criteria will be offered to roll over into an open label extension study.

Figure 1. Trial Design

BI 655066 is risankizumab.

